Engaging clinical champions to Improve HPV Vaccination

Hypotheses and Analytic Plan

NCT# 05736718

Version date: 3/15/2023

Analysis plan for HPV vaccine champion trial

The purpose of this cluster randomized non-inferiority trial is to compare Champion Announcement Approach Training (AAT) to Traditional AAT on HPV vaccine initiation among patients ages 9-12.

Hypotheses

The primary hypothesis is that Champion AAT will be non-inferior to Traditional AAT for increasing HPV vaccine initiation. By engaging highly influential physicians, we anticipate that Champion AAT will be at least as effective as Traditional AAT for increasing HPV vaccine uptake.

Design & Power

We will randomize 40 clinics within multiple healthcare systems to the two trial arms (Champion vs Traditional AAT). To maximize balance in trial arms, we block randomization by system in a 1:1 ratio.

With 20 clinics per study arm, we will have $\geq 80\%$ power to conclude non-inferiority of Champion vs Traditional AAT when Champion AAT increases HPV vaccine uptake $\geq 8\%$ points over the secular trend. This calculation assumes: 1) a clinic-level ICC of .033 for change in HPV vaccine initiation, as observed in our pilot work; 2) a non-inferiority margin of .04; 3) 100 patients, ages 9-12, per clinic on average; 4) a secular trend of 10% points; and 5) Traditional AAT effect of 5% points, as observed in our prior trial.³⁵ Achieving an effect size of $\geq 8\%$ points with Champion AAT is feasible, given that we are modeling HPV vaccination among unvaccinated adolescents, whose uptake will be higher proportionally than the general population.

The non-inferiority margin, delta, will be .04, which we have selected to detect any clinically meaningful difference between the effectiveness of our interventions. To test for non-inferiority with a margin of .04, we will translate the lower and upper 95% confidence interval limits into predicted probability units and conclude that Champion AAT is inferior if the transformed upper confidence limit falls below .04.

Analytic Plan

Primary trial outcome: HPV vaccine initiation by 12-month follow-up

We will assess the vaccination status of adolescents who are HPV vaccine naïve at baseline, using routinely collected EHR data from our healthcare systems and submitted to the Wisconsin Collaborative for Healthcare Quality.

We will model HPV vaccine initiation using a generalized estimating equation (GEE) for logistic outcomes. GEE models accommodate non-independence due to nesting of patients within clinics by adjusting standard error terms. The outcome of the model will be patient-level HPV vaccine initiation at follow-up (0=no, 1=yes):

$$\ln\left(\frac{p(vax_{2ij})}{1 - p(vax_{2ij})}\right) = b_0 + b_1 Champion_j + b_2 System_j$$

Trial arm will be the primary fixed effect as a two-level, categorical variable (Champion AAT vs. Traditional AAT). Since we will be block randomizing on healthcare system, system membership will be added as an n-level, categorical covariate where n is the number of participating systems. Tests will be 2-tailed with $\alpha=.05$ Statistical analyses will be conducted in SAS 9.4 (Cary, NC) and R 4.2.2.

Missing Data

We will use all available data in computing the primary outcome of HPV vaccine initiation by 12-month follow-up as per our intent-to-treat protocol. We will drop the clinic if no data are available (e.g., due to clinic closure).

Adjustment for covariates

We do not plan to adjust for demographic or other baseline characteristics per CONSORT recommendations (Consort, 2010).

Secondary trial outcome

The secondary trial outcome is HPV vaccination series completion (2 doses) at 12 months, which we will evaluate in the same manner as the primary outcome.

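### The rule for setting logistic confidence limits against the absolute .04 margin is unspecified, and read literally it places the deciding limit too close to zero.

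*SAP*

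**What the plan says.** In the SAP, Design & Power, the margin is given as a plain number: "The non-inferiority margin, delta, will be .04". The power inputs beside it (secular trend 10, Traditional effect 5, Champion effect 8) are all in percentage points. To apply the margin, the same section states: "we will translate the lower and upper 95% confidence interval limits into predicted probability units".

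The primary outcome model is in Analytic Plan: "We will model HPV vaccine initiation using a generalized estimating equation (GEE) for logistic outcomes". It has an intercept, one arm coefficient b1 and a system term: "system membership will be added as an n-level, categorical covariate where n is the number of participating systems". There is no arm-by-system interaction. The model therefore yields one log odds ratio for arm and a separate baseline rate for each system.

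The SAP does not say at which rate the limits are converted, whether predictions are averaged over systems, or how the sampling error of the baseline enters the interval. Under Secondary trial outcome, series completion is to be analysed the same way, so it inherits the gap.

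**The concern.** A limit for a log odds ratio has no value as a difference in probabilities until it is attached to a baseline rate. Two things follow.

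- **Variance.** The literal operation takes the two limits of b1 and maps them through the inverse logit at an estimated baseline. That baseline is then treated as known. Its own error is part of the risk difference, and near the margin the mapping gives it too little weight.
- **Anchor.** With a system factor there are as many baselines as systems. If one of them serves as the anchor, the same odds-ratio limit gives a different absolute difference for each choice, yet all are compared with one fixed margin.

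This sentence is the bridge between the fitted model and the primary conclusion. As written, the choice of conversion could be made after the data are seen. The point is separate from which limit and which sign that sentence uses, and it remains once those are settled. The calculations below therefore use the conventional rule: non-inferiority if the lower limit of Champion minus Traditional exceeds -.04.

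**Working it through.** **Inputs from the SAP.** "With 20 clinics per study arm"; "100 patients, ages 9-12, per clinic on average"; ICC .033; margin .04; two-sided alpha .05, hence .025 on the deciding limit; Traditional rate .10 + .05 = .15; Champion rate .10 + .08 = .18. Allocation: "we block randomization by system in a 1:1 ratio". The number of systems and their rates are not given and are assumed where used.

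**1. The plan's power figure.** Design effect 1 + 99 × .033 = 4.267. Effective n per arm = 2000/4.267 = 468.7. SE = √[(.15×.85 + .18×.82)/468.7] = .0242. Power = Φ[(.03 + .04)/.0242 − 1.96] = 82.4%, or 80.4% with t on 38 df. The stated figure of at least 80% is reproduced, which confirms that .04 is an absolute difference.

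**2. Dependence on the reference rate.** The converted limit is expit(logit r + ln OR) − r. If both arms are observed at .15, SE(b1) = √[2/(468.7 × .1275)] = .183 and the OR interval is 0.699 to 1.431. Its lower limit becomes:

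| Reference rate r | Lower limit as a difference |
|---|---|
| .10 | -.0280 |
| .15 | -.0402 |
| .20 | -.0513 |
| .25 | -.0611 |

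The first passes a -.04 margin and the last two clearly fail. Conversely, a difference of -.04 is an OR of 0.574 at .10, 0.700 at .15 and 0.797 at .25.

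**3. Effect of treating the baseline as known.** Take one common rate, p0 = .15, and a true difference of -.04, so p1 = .11. Then p0q0 = .1275 and p1q1 = .0979.

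- Correct SE of the difference: √[(.0979 + .1275)/468.7] = .0219.
- SE(b1) = √[1/(468.7×.1275) + 1/(468.7×.0979)] = .1963. On the probability scale the literal conversion uses about p1q1 × SE(b1) = .0979 × .1963 = .0192, which is too small.
- Non-inferiority is declared when logit(p̂1) − logit(p̂0 − .04) > 1.96 × .1963 = .3847. At the boundary the left side has mean about 0 and SD about .0219/.0979 = .2240. The error rate is about 1 − Φ(.3847/.2240) = 1 − Φ(1.717) = 4.3%, against 2.5%.

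Comparing limits with p0 = .15:

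| Difference | Literal conversion | Wald risk difference | Widths |
|---|---|---|---|
| -.04 | -.0724 to .0037 | -.0830 to .0030 | .0761 v .0860 |
| 0 | -.0402 to .0516 | -.0457 to .0457 | .0919 v .0914 |
| +.03 | -.0156 to .0868 | -.0175 to .0775 | .1024 v .0950 |

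The lower limit is closer to zero in every row. The total width is not smaller in every row.

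**4. Simulation.** 40 clinics × 100 patients, ICC .033, logistic model with arm and system, clinic-robust variance, 3000 or 4000 trials per scenario. The Monte Carlo SE near 2.5% is about √(.025×.975/3000) = 0.3 points. False non-inferiority at a true mean difference of about -.04:

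| Conversion and assumed rates | Literal conversion | Delta-method risk difference |
|---|---|---|
| One common 15% rate (four runs) | 4.0-4.8% | 2.0-2.8% |
| Averaged over systems, rates 12-18% or 10/20% | 3.4-4.0% | 1.6-2.3% |
| Averaged over systems, no small-sample correction, all at 15% or 8-22% | 5.3-5.4% | 2.9-3.2% |

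If a single system's intercept is the anchor and the arms are truly equal, the verdict differed between reference systems in 33-34% of trials with rates 12/14/16/18%. It differed in 21-22% with every system at 15%, where only noise in the fitted baselines separates them. A wider assumed spread, 8% to 22%, gave 60%.

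**5. Power with the corrected interval.** At 18% v 15%: 79-80% with one common rate and about 76-77% with rates 12-18% (leverage-corrected variance, t limits). It was 81% with rates 8-22% at the planned odds ratio of 1.244 without that correction.

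**The case against.** The strongest reply is that the SAP does not describe the procedure being criticised. It does not say that the limits are those of b1, that the intercept is the anchor, or that the baseline is held fixed. Predicted probabilities averaged over systems also fit the wording and do not depend on coding. This stands in part. A reader might infer that the verdict will depend on how system is coded; the documents support only that it can, because the choice is left open. Averaging removes that dependence, but it does not remove the anti-conservatism if the limits of b1 are what is converted.

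A reader might also infer that the whole interval is too narrow. It is not: the literal interval is about as wide as the Wald interval at no difference, and wider at the planned +.03. Only the lower limit is consistently too close to zero.

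Finally, anchoring at the lowest-rate system gave false non-inferiority of 13.8% (rates 12-18%) and 25.2% (rates 10/20%) in one simulation. These should not be read as pure type I error. Under those assumptions the true difference in the 12% system is -.033 and in the 10% system -.028, both inside the margin, so the figures mostly reflect a changed target.

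**Conclusion.** The concern holds in this form: the conversion from the logistic model to the absolute margin is not specified, and its literal reading is anti-conservative on the limit that decides non-inferiority. The false non-inferiority rate is about 3.5-5% against a nominal 2.5%. The closed-form 4.3% rests on the SAP's own inputs alone (one common rate of 15%). The simulated range also rests on assumed system rates and on the small-sample correction used.

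Dependence on the reference system is conditional on a single-intercept anchor. Under that reading about 20-33% of equal-arm trials change verdict; this figure depends on the assumed number of systems and their rates, neither of which the SAP gives. The effect on the error rate is modest, but it bears on the primary conclusion and is easily removed before analysis.

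**What to change.** Replace the conversion sentence in Design & Power with text such as:

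*From the fitted GEE we will estimate the marginal risk difference (Champion minus Traditional) by standardisation: predict each analysed patient's probability of initiation under each arm, keeping the patient's own system, average over all analysed patients, and subtract. The 95% confidence interval will use the delta method with the full cluster-robust covariance of all coefficients (or a clinic bootstrap within system and arm). Non-inferiority will be concluded if the lower limit exceeds -.04.*

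State that the secondary outcome is handled the same way.

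The cost is SAP wording and a few lines of SAS or R, with no new data. The interval reaches slightly further on the deciding side, so power at 18% v 15% is borderline, about 76-81% depending on system rates and small-sample correction. The stated power of at least 80% should be described as approximate.

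### The only non-inferiority rule compares the upper confidence limit with +.04: at the planning values it calls two identical arms inferior about 40% of the time, and no criterion for non-inferiority is stated

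*SAP*

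**What the plan says.** - **Hypotheses:** the primary hypothesis is that "Champion AAT will be non-inferior to Traditional AAT for increasing HPV vaccine initiation".
- **Design & Power:** "The non-inferiority margin, delta, will be .04". Power of at least 80% is claimed, described as "power to conclude non-inferiority of Champion vs Traditional AAT".
- **Design & Power, last paragraph:** for the test, "we will translate the lower and upper 95% confidence interval limits into predicted probability units", and the analyst is then to "conclude that Champion AAT is inferior if the transformed upper confidence limit falls below .04". The lower limit is transformed but never used, and nothing says what result establishes non-inferiority.
- **Analytic Plan:** the linear predictor is "b_0 + b_1 Champion_j + b_2 System_j", with initiation coded 1 for yes. A positive arm coefficient therefore favours Champion. Tests are two-tailed at .05.
- **Secondary trial outcome:** series completion is to be evaluated in the same way as the primary outcome, so it inherits the rule.

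**The concern.** When higher is better and the contrast is Champion minus Traditional, non-inferiority with margin .04 means ruling out a deficit of .04 or more: the lower 95% limit must lie above −.04. The printed rule uses the other limit and the other sign, and attaches the label *inferior* to the result. An interval from −1 to +3 points establishes non-inferiority, since its lower limit is above −4, yet the rule calls it inferior because its upper limit is below +4.

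This is the trial's only primary decision rule. Followed literally it can return the opposite of what the data show, and the risk grows with precision when the true difference is near zero. If it is instead mended informally at analysis, the choice among several possible corrections would be made with the data in view.

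**Working it through.** **Inputs, all from the SAP.** 20 clinics per arm; 100 patients per clinic on average; ICC .033; margin .04; secular trend 10 points; Traditional effect 5 points, so Traditional rate .15; Champion effect 8 points, so Champion rate .18 and true difference +.03; two-sided 95% interval.

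**Precision**
- Design effect = 1 + 99 × .033 = 4.267.
- Effective n per arm = 2000 / 4.267 = 468.7.
- SE at .15 and .18 = √[(.15×.85 + .18×.82) / 468.7] = .0242.
- SE at .15 and .15 = √[2×.15×.85 / 468.7] = .0233.

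**The plan's own power figure.** Under the standard rule (lower limit of Champion − Traditional above −.04), power = Φ((.03 + .04)/.0242 − 1.96) = 82.4%, or 80.4% with a t reference on 38 df. The requirement is 441 × 4.267 = 1882 patients, or 18.8 clinics per arm, against 20 planned. The claim of at least 80% is reproduced, and this is the rule that reproduces it.

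**The printed rule.** With true difference d, P(upper limit < +.04) = Φ((.04 − d)/SE − 1.96).

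| True d (Traditional .15) | SE | Called inferior as written | Non-inferior by standard rule |
|---|---|---|---|
| −.04 | .0219 | 95.4% | 2.5% |
| 0 | .0233 | 40.3% | 40.3% |
| +.03 | .0242 | 6.1% | 82.4% |

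At equality the half-width is 1.96 × .0233 = .0457. The rule is therefore met whenever the observed difference is below .04 − .0457 = −.0057, a shortfall of about 0.6 points.

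**Sensitivity for identical arms**
- Common rate .10: 53%; .18: 36%; .30: 27%.
- ICC .01: 71%; .02: 54%; .05: 31%. The smaller the ICC, and so the tighter the interval, the more often equal arms are called inferior.
- t reference on 38 df: 38.7%.
- Beta-binomial cluster simulation (40,000 trials): 41% with a risk-difference interval; 34% when log-odds-ratio limits are converted at the observed Traditional rate.

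**Other readings of the sentence**
- *Traditional − Champion.* An upper limit below .04 is then exactly the non-inferiority criterion, so the conclusion is reversed. Identical arms are still called inferior 40.3% of the time, and at the design alternative Champion is called inferior 82.4% of the time.
- *.04 meant as −.04.* This is a test of proven inferiority; identical arms would meet it about 0.01% of the time. If failing to meet it were taken as non-inferiority, a Champion arm truly 4 points worse would pass with probability 1 − .025 = 97.5%, instead of 2.5%.
- *Limit taken as an arm's predicted probability.* With rates near .15 to .18, an upper limit below .04 would almost never occur, so the rule would decide nothing.

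**The case against.** The strongest reply is that this is a drafting slip whose intent is recoverable. The hypothesis, the margin, the two-tailed alpha and the power figure all point to the standard rule. The SAP never defines the difference explicitly, and if Traditional − Champion was meant, the limit and sign are right and only the word *inferior* is wrong. That much is fair: which slip occurred cannot be settled from the text. But a missing minus sign and a wrong word need different corrections and can give different verdicts on the same data, so the sentence cannot safely be left to the analyst. The only coding shown in the SAP is Champion against Traditional.

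The 40% is also conditional. It assumes a risk-difference interval and a common rate of 15%, and the SAP itself expects proportionally higher uptake among unvaccinated adolescents. At 30% it is 27%, still far above any acceptable error rate.

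The −1 to +3 interval illustrates the logic but is narrower than planned: the expected half-width is about 4.6 points. At planned precision, and with Champion − Traditional, the usual error would be to label an inconclusive interval, such as −6 to +3, inferior. The 97.5% belongs to an altered rule and shows only that inserting a minus sign is not a sufficient repair.

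Finally, rewording the threshold alone does not fix how logit-scale limits become a difference. In the simulation, false non-inferiority at a true −4 points was 3.0% with a risk-difference interval and 5.4% with transformed log-odds-ratio limits. That point stands and is taken into the fix.

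**Conclusion.** The concern holds. The printed rule is not a valid non-inferiority rule under any of the readings considered, it does not match the SAP's own power statement, and the SAP contains no usable condition for concluding its primary hypothesis. Taken literally with Champion − Traditional, it calls identical arms inferior about 40% of the time and a truly better Champion arm (+3 points) inferior about 6% of the time. These figures rest on a 15% Traditional rate, ICC .033, 20 clinics of 100 per arm and a normal-approximation risk-difference interval; for identical arms the range is 27% to 53% over common rates of 30% to 10%. The sample size is not at fault. This must be corrected before the data are analysed.

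**What to change.** Replace the sentence in Design & Power with:

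> Let D = P(initiation | Champion) − P(initiation | Traditional). Conclude non-inferiority if the lower limit of the two-sided 95% confidence interval for D is above −.04. Conclude inferiority only if the upper limit is below −.04. Otherwise the result is inconclusive.

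Add one sentence on how the interval for D is obtained from the logistic GEE. For example: predicted probabilities under each arm averaged over the observed system mix, with a delta-method standard error from the robust covariance. State that the same rule and direction apply to series completion, or give that outcome its own rule.

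The cost is a few lines of SAP text. No data collection, sample size or power claim changes, because the stated power already corresponds to the corrected rule.

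### The SAP sets no small-sample variance correction or t reference for its 40-clinic GEE; run in the ordinary way, the 95% interval behind the primary conclusion under-covers

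*SAP*

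**What the plan says.** Under Design & Power, the SAP states: "We will randomize 40 clinics within multiple healthcare systems to the two trial arms". Allocation is blocked by system, 20 clinics per arm, with "100 patients, ages 9-12, per clinic on average". Non-inferiority is to be judged from the model's interval: "we will translate the lower and upper 95% confidence interval limits into predicted probability units".

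Under Analytic Plan (Primary trial outcome), the model is a logistic GEE with arm and system as its only terms. On clustering the SAP says "GEE models accommodate non-independence due to nesting of patients within clinics by adjusting standard error terms". On system it says "system membership will be added as an n-level, categorical covariate where n is the number of participating systems"; n is not given. On software: "Statistical analyses will be conducted in SAS 9.4 (Cary, NC) and R 4.2.2", with no procedure or option.

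Under Missing Data, the number of clusters may fall: "We will drop the clinic if no data are available (e.g., due to clinic closure)". The secondary outcome, series completion, is to be evaluated by the same method.

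**The concern.** The sentence on clustering is correct as a general description of GEE. What it leaves open is how the standard error is estimated and which distribution supplies the limits. The usual sandwich estimator is justified by a large number of clusters. It is built from residuals that are too small on average, because the fitted model has already used some of the between-clinic variation. Arm and system are both clinic-level, so each system added takes another degree of freedom from 40 clinics, not from some 4,000 patients.

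The interval decides the primary question, so its width matters directly. With the method left open, defensible analyses of the same data give different widths, and nothing in the SAP prevents the choice from being made after results are seen.

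**Working it through.** **Inputs from the SAP (Design & Power).** 20 clinics per arm; 100 patients per clinic; ICC .033; margin .04; Traditional uptake .10 + .05 = .15; Champion uptake .10 + .08 = .18; two-sided 95% interval.

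**Assumed, because the SAP does not say.** Number of systems S = 2, 3, 5 or 10; clinic-size CV of 0 or 0.6; arms balanced within system; no system effects.

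**1. The SAP's power figure.** Design effect = 1 + 99 × .033 = 4.267. SE = √[(.18 × .82 + .15 × .85) × 4.267 / 2000] = .0242. (.03 + .04)/.0242 = 2.89. Power is 82.4% with normal limits. With noncentral t it is 80.3% on 37 df and 79.8% on 29 df. The stated figure of at least 80% is reproduced, with almost no reserve once t limits are used.

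**2. Degrees of freedom.** Intercept, arm and S − 1 system indicators make S + 1 clinic-level parameters, leaving 40 − S − 1: 37, 36, 34 and 29.

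**3. Closed-form coverage.** With equal sizes the analysis behaves approximately like a regression of clinic proportions on arm and system. The uncorrected SE is then too small by about √(df/40), so coverage ≈ P(|t on df| < 1.96 × √(df/40)).

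| Systems | df | √(df/40) | 1.96 × factor | Coverage |
|---|---|---|---|---|
| 2 | 37 | .962 | 1.885 | 93.3% |
| 3 | 36 | .949 | 1.859 | 92.9% |
| 5 | 34 | .922 | 1.807 | 92.0% |
| 10 | 29 | .851 | 1.669 | 89.4% |

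**4. Simulation of the SAP's model.** Beta-binomial data, logistic GEE with arm and system, standardised risk difference with delta-method SE, 40,000 runs per scenario (Monte Carlo SE about 0.1 points for coverage, 0.2 for power). True rates are .11 against .15, a difference equal to the margin. KC is Kauermann-Carroll. The first four result columns are for equal sizes.

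| Systems | Coverage, uncorrected z | Coverage, uncorrected SE with t | Lower limit above the true difference (nominal 2.5%) | Mean half-width, uncorrected z / KC with t | Coverage, uncorrected z, CV 0.6 exchangeable |
|---|---|---|---|---|---|
| 2 | 93.4% | 94.3% | 3.3% | .0410 / .0440 | 93.1% |
| 3 | 92.8% | 93.7% | 3.7% | .0404 / .0441 | 92.7% |
| 5 | 91.9% | 92.9% | 4.1% | .0392 / .0442 | 91.5% |
| 10 | 89.3% | 90.7% | 5.2% | .0361 / .0444 | 88.4% |

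Coverage agrees with step 3. At the planning rates (.18 against .15) it is 93.6%, 92.7%, 92.1% and 89.2%. KC with t covers 95.0-95.1% with equal sizes and 94.5-94.9% with CV 0.6 and exchangeable correlation. The half-width gap runs from .0440 − .0410 = .0030 to .0444 − .0361 = .0083, or 7.5% to 21% of the .04 margin.

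**5. Power at .18 against .15.** Success is taken as a lower limit above −.04, which is an assumption (see the objection).

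| Systems | Uncorrected z, equal sizes | KC with t, equal sizes | KC with t, CV 0.6 exchangeable | Loss from unequal sizes |
|---|---|---|---|---|
| 2 | 84.1% | 80.3% | 77.5% | 2.8 |
| 3 | 84.4% | 80.2% | 77.9% | 2.3 |
| 5 | 86.0% | 80.5% | 77.7% | 2.8 |
| 10 | 88.8% | 80.0% | 76.9% | 3.1 |

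With equal sizes the correction costs 3.8 (84.1 − 80.3) to 8.8 points (88.8 − 80.0). Much of that is power the too-narrow interval only appeared to have.

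**The case against.** **The SAP never says it will use the uncorrected sandwich.** True. A reader might infer that it commits to an invalid interval, but both named packages leave the choice open and no printed statement is wrong. The point is that the ordinary way of running the model under-covers and nothing in the SAP rules it out. That someone would choose the method after seeing results is possible, not shown.

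**The harm need not be a false claim of non-inferiority.** A reader might infer that a narrow interval makes such a claim too easy. That follows if non-inferiority means a lower limit above −.04. Design & Power prints a different rule: Champion is called inferior if the upper limit falls below .04. Read literally, a narrower interval then gives more verdicts of inferiority. An approximate simulation at equal true rates of .15 with 2 systems gave 44.4% uncorrected against 39.1% corrected. This objection stands: the direction of decision error is not firm until the rule is settled, whereas coverage needs no decision rule.

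**The size rests on unstated figures.** Also true. With 2 or 3 systems the loss is about 2 points, and 89% needs 10 systems averaging four clinics each. The 10-system case should not set the priority.

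**The remedy is not perfect either.** With 2 systems and equal sizes, t limits on the uncorrected SE already cover 94.3%, which is nearly enough; they fall short with more systems. In a separate simulation on the log-odds scale, Kauermann-Carroll with t fell to 93.4% with size CV 0.8 and independence. It is better than the uncorrected interval, not exact.

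**Conclusion.** The point holds as an under-specification with a demonstrable consequence. The method that sets the width of the primary interval is not fixed. The ordinary choice covers about 93% with 2-3 systems, 92% with 5 and 89% with 10, given equal sizes, ICC .033 and 100 patients per clinic. Dropping clinics lowers this slightly: with 4 of 40 lost at random (assumed), coverage is 93.0%, 92.6% and 91.1% for 2, 3 and 5 systems.

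If non-inferiority is judged by a lower limit above −.04, the one-sided error is about 3.3-3.7% with 2-3 systems and about 5-6% with 10, instead of 2.5%. That is conditional on a rule the SAP does not print.

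A reader might also infer that the power claim "power to conclude non-inferiority of Champion vs Traditional AAT when Champion AAT increases HPV vaccine uptake" is wrong. It is not: with the correction and equal sizes, simulated power is 80.0-80.5%. Figures below that come from assumed size variation or lost clinics, not from this omission. The gap should be closed before analysis, but it does not invalidate the design.

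**What to change.** Add one statement covering both outcomes, for example: *Standard errors will be small-sample bias-corrected (Kauermann-Carroll), with t limits on degrees of freedom equal to analysed clinics minus clinic-level parameters, and an exchangeable working correlation.* This is one accepted choice. Mancl-DeRouen with t also controls error but is conservative: coverage 96.0-97.9% and power falling from 78.0% to 68.7% as systems rise from 2 to 10, with equal sizes.

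The working correlation makes no difference with equal sizes, but it should still be named in advance. If clinic size may be related to uptake, exchangeable and independence target different averages, so the SAP should say which is meant. That is a separate choice of estimand, not part of the coverage problem.

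The cost is a sentence, a software option or short R call, and a rerun of the power calculation with the number of systems and the expected spread of clinic sizes. The half-width grows by about .003 to .008. Simulated power is about 80% with equal sizes, about 77-78% with size CV 0.6 and exchangeable correlation, and 75-76% if 4 equal-sized clinics are lost (2 to 5 systems).
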